This visit should occur no more than 7 days after the Screening Visit. Any subject who returns but does not qualify at this visit will be a screen failure and will not be randomized. Upon completion of all screening procedures and confirmation that the subject is eligible for the study, the Investigator or designee will randomize the subject using an electronic randomization system (www.sealedenvelope.com) to obtain the treatment assignment.

The day of the week (Monday, Tuesday, etc.) on which this visit occurs will set the weekly visit day for all subsequent assessments/visits (Study Visits 2 through 7) if the subject is randomized. A (± 1) day visit window will be allowed. If an assessment is not made on the original day of the week for Study Visits 2-7, subsequent visits should be scheduled on the original week day. To minimize differences in baseline ulcer size between the two groups, randomized subjects will be stratified by ulcer size determined at this visit [≥ 1.0 and ≤ 10.0 cm²; ≥ 10.0 and ≤ 64.0 cm²]. Once randomized, subjects will be assessed weekly for the duration of the treatment period (SV1 through SV7).

The following procedures will be completed:

- 1. Record any changes in general health and the use of concomitant medications.
- 2. If any adverse events are observed or reported, they must be recorded as instructed in Section 12, *Adverse Events*.
- Review laboratory results from the blood sample and all other inclusion/exclusion
 criteria.
 - If the blood test results qualify and all entry criteria are met, the subject may be randomized.
- Irrigate the wound with normal saline delivered at 4-15 psi using the Irrimax® device.
 (Sharp debridement is NOT allowed.)
- 5. Photograph the target ulcer using the ImageIQ EDCIQ mobile imaging system. The target ulcer area (cm²) and percentage of the target ulcer surface covered with necrotic, nonviable tissue will be determined by two independent reviewers using the ImageIQ EDCIQ mobile imaging system. The target ulcer area and percentage of necrotic, nonviable tissue must be assessed by at least one independent reviewer prior to the subject being randomized.

Note: If the area of the target ulcer is >64.0 cm², the subject must be screen failed and should not be randomized.

- 6. Assess the wound status using both the PUSH and WBS tools.

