9.1.3 Study Visits 2-6

Study Visits 2-6 are post-randomization weekly assessments during the treatment period. During this period, all adverse events must be recorded, including those associated with treatment, study procedures, or concomitant medication. All weekly visits must be performed according to the study visit schedule (Table 17-1), preferably on the same day each week. Subjects found to have wound closure at a weekly assessment should **NOT** complete that visit but instead go directly to Study Visit 7 (Exit Visit), be discontinued from treatment and have exit procedures performed. A closed ulcer is defined as having complete re-epithelialization, without drainage or the need for a dressing. All study procedures should occur in the order outlined in the protocol. Visits occurring outside the visit window should be completed and recorded as a protocol deviation.

- If the ulcer is closed at this assessment visit, do not complete these procedures. Instead go directly to Study Visit 7 (Exit Visit).
- 2. Record any changes in general health and the use of concomitant medications.
- If any adverse events are observed or reported, they must be recorded as instructed in Section 12, Adverse Events.
- Record the number of dressing changes since the previous study visit and the amount of time spent daily dressing the ulcer.
- Irrigate the wound with normal saline delivered at 4-15 psi using the Irrimax[®] device.
 (Sharp debridement is NOT allowed.)
- Photograph the target ulcer using the ImageIQ EDCIQ mobile imaging system. The target ulcer area (cm²) and percentage of the target ulcer surface covered with necrotic,

- nonviable tissue will be determined by two independent reviewers using the ImageIQ EDCIQ mobile imaging system.
- Ensure that all caregivers are instructed as to the treatment requirements for the study
 protocol and that they are instructed in the application of test article and dressing changes.
 Ensure adequate supplies (test article and dressings) are dispensed.
- Apply the test article to the entire wound bed according to the instructions for use located in the Study Guide, cover with a semi-occlusive dressing (e.g. COVRSITETM). If the wound has depth, saline moistened gauze may be used to fill at the Investigator's discretion.
- 9. Record the time spent dressing the ulcer at this visit.
- Schedule the next weekly assessment in 7 (±1) days.

9.1.4 Exit Visit - Study Visit 7

This is the final visit for all subjects in the study.

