9.2 DISCONTINUED SUBJECTS

Discontinued subjects are those who voluntarily discontinue participation, who are withdrawn for safety reasons or use of prohibited concomitant treatments. In all cases the Exit Visit (Study Visit 7) must be completed.

All subjects who discontinue the study prior to completing the regularly-scheduled visits should complete the exit visit procedures described in Section 9.1.4. If appropriate, the Investigator also should advise the subject of subsequent therapy and/or procedures necessary for their medical condition.

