10.3.2 Secondary Efficacy

The secondary efficacy variables include the time (in days) to achieve complete debridement, the percentage reduction in non-viable necrotic tissue for each assessment visit, and the percentage reduction in ulcer area for each visit and the change in wound status as measured by the PUSH and WBS tools following 6 weeks of treatments.

Time (in days) to achieve complete debridement during the 6-week treatment period (with complete debridement as defined in the primary analysis)

Once a subject has achieved complete debridement, the time to complete debridement will be calculated from the date of the randomization visit to the date at which the subject's ulcer was deemed to achieve complete debridement:

(Date of first complete debridement visit - Date of Randomization (SV1))

For those subjects that withdraw or do not achieve complete debridement during the study, the time to complete debridement will be censored at the last visit date attended. The resulting time to complete debridement will be defined as:

(Date of Last Study Visit attended - Date of Randomization (SV1))

Where the censored time to complete debridement is greater than 42 days, this will be truncated to 42 days.

A proportional hazards survival analysis will be applied to the time to achieve complete debridement using the Full Analysis Set. An initial proportional hazards model will include the covariates for treatment, baseline (defined as Study Visit 1) ulcer area, baseline percentage of nonviable tissue, and duration of ulcer. A forward selection procedure will be used for the addition of other baseline covariates with an F-value to attain a significance level of 0.1. Further baseline covariates to be assessed as part of this procedure include: subject age, baseline (maximum) ulcer depth, baseline PUSH and WBS scores. The resulting analysis presented will correspond to the final model from the forward selection procedure. The results for the initial model will also be presented. For each of the effects in the initial and final model, the p-value, hazard-ratio and corresponding 95% confidence interval will be presented. Secondary subgroup analyses may be conducted as a result of the covariate analyses. Additionally, treatment will be fitted on its own in a further proportional hazards survival analysis.

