Further details, including model assumptions and diagnostics to be examined are included in the study SAP. The preceding analysis will be repeated using the Per Protocol Population.

Kaplan-Meier plots will be presented by treatment, baseline wound area strata, baseline percentage of nonviable tissue and ulcer duration (categorized) and also to represent all covariates with significant effects in the final survival analysis model. Individual plots for multiple factors will be generated where appropriate.

In addition, a sensitivity analysis will be performed to ensure that the efficacy findings are not reliant on assumptions made in either the analysis or derivations. For purposes of the sensitivity analysis, the time to confirmed complete debridement for those subjects discontinuing the treatment period prematurely will be censored at the maximum possible duration of treatment under the study protocol (42 days), rather than time of actual discontinuation. Lastly, the two sensitivity analyses defined in the proportion of subjects achieving complete debridement analysis will be repeated for the time to achieve complete debridement; in these cases the

censoring flag may be modified as detailed previously in the primary analysis, but the time in days will remain unchanged.

The percentage reduction in wound area over the 6-week treatment period and at each assessment visit

Wound area is defined as surface area as measured by the ImageIQ EDCIQ mobile imaging system at each assessment visit by two independent image reviewers. The percentage change in wound area over the 6-week treatment period is then defined as:

Percentage reduction in wound area over 6-week treatment period= $\left(\frac{Area_{SV1} - Area_{SV1}}{Area_{SV1}}\right) \times 100\right)$

In cases where the wound is closed in the opinion of the Investigator, the wound area will be imputed as 0 cm², resulting in a percentage reduction in wound area of 100%. In circumstances where the wound area is missing at the Study Visit 7 for subjects that have not withdrawn prematurely due to closure, the last observation carried forward (LOCF) method will be used.

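### Only censored times are capped at 42 days, so one debridement dated after day 42 takes that arm's Kaplan-Meier curve to 0% un-debrided

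*Combined protocol and SAP*

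**What the plan says.** Section 10.3.2 of the protocol times an event as "Date of first complete debridement visit - Date of Randomization (SV1". A subject who withdraws or is never debrided is censored at the last visit attended, and then: "Where the censored time to complete debridement is greater than 42 days, this will be truncated to 42 days". No cap on event times appears anywhere in the text supplied.

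Section 9.1.2 fixes the visit weekday at Study Visit 1 and adds "A (± 1) day visit window will be allowed". After an off-day visit, "subsequent visits should be scheduled on the original week day". Visit 7 is therefore nominally day 42 and may fall on days 41 to 43. Section 9.1.3 has visits outside the window completed and logged as deviations, so later dates can also arise. Necrotic tissue is read from the Visit 7 photograph (section 9.1.4), so a first complete debridement can be dated there.

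Section 10.3.2 also plans the display: "Kaplan-Meier plots will be presented by treatment, baseline wound area strata", with further plots by baseline non-viable tissue, ulcer duration and significant covariates. For the two sensitivity analyses on disagreement between the image readers, the "censoring flag may be modified as detailed previously in the primary analysis, but the time in days will remain unchanged".

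**The concern.** Take two subjects, both seen at a Visit 7 on day 43. The debrided one is given 43 days and the un-debrided one 42. The second has left the risk set before the first has the event, although both were under observation on the same day.

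Every censored time is thus at most 42, so the risk set after day 42 contains only subjects who themselves have late events. The plotted curve for that arm, or for any other plotted group with a late event, ends by showing everyone debrided. The plan's own assumptions leave 15% (SANTYL) and 71% (hydrogel) not debrided. If no first debridement in a group is dated after day 42, its curve is unaffected.

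**Working it through.** **Inputs.** Timing rules: section 10.3.2. Visit window: section 9.1.2. Debridement rates of 85% and 29%, 16 per arm and 15% drop-out: section 11. The event days and the share of Visit 7s on day 43 are assumptions, because the documents do not give them.

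**Arm size.** Two-sided Fisher's exact power at 13 per arm for 85% vs 29% is 80.9% (74.2% at 12 per arm), which agrees with the stated 26 if 80% power was meant; the plan states no power. 26/0.85 = 30.6, so 31, or 32 when balanced: 16 per arm, as planned.

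**Algebra.** The product-limit factor at an event time is 1 − d/n (d events, n at risk). At the last event after day 42, n = d, so the factor is 0 and S(t) = 0. This depends on no assumed rate.

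**Hydrogel example.** 16 subjects, events on days 14, 21, 28, 35 and 43, and 11 un-debrided subjects all followed to day 42 or later.
- As written: 15/16, 14/16, 13/16, 12/16 = 75%. On day 43 there is 1 at risk and 1 event, giving 0%.
- Both truncated: 12 at risk and 1 event on day 42, so 0.75 × 11/12 = 68.75%.
- Neither truncated, with k of the 11 last seen on day 43 or later: 0.75 × k/(k+1) = 0%, 37.5%, 50%, 62.5%, 68.75% for k = 0, 1, 2, 5, 11.
- Both truncated, but 3 of the 11 last seen on day 41: 0.75 × 8/9 = 66.7%.

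**Two late events** (days 14, 21, 28, 43, 45; 11 censored), as written: 81.25%, then 40.6%, then 0%.

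**SANTYL example.** 14 of 16 debrided, one on day 43, 2 censored. As written: 3/16 = 18.75%, then 0%. Both truncated: 2/16 = 12.5%.

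**How often.** Assume constant weekly hazards: 1 − 0.15^(1/6) = 0.2711 and 1 − 0.71^(1/6) = 0.0555. The probability p of a first debridement at week 6 is then 0.0558 (SANTYL) and 0.0417 (hydrogel). With q the share of Visit 7s on day 43 and r the share retained to Visit 7, the chance of at least one late event in an arm is 1 − (1 − pqr)^16.

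| q | SANTYL, r = 1 | Hydrogel, r = 1 | Either arm, r = 1 | Either arm, r = 0.85 |
|---|---|---|---|---|
| 5% | 4.4% | 3.3% | 7.5% | 6.4% |
| 10% | 8.6% | 6.5% | 14.5% | 12.4% |
| 20% | 16.4% | 12.5% | 26.9% | 23.4% |
| 33% | 25.9% | 20.1% | 40.8% | 35.9% |

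**Cox model.** A lone event after day 42 across both arms is compared only with itself and contributes a factor of 1 to the partial likelihood, so its information is lost. The average effect was simulated with 600 trials per q and 15% drop-out, fitting treatment plus three null covariates with Efron ties. Some fits gave convergence warnings, and forward selection was not modelled.

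| q | Power, as written vs both truncated | Median hazard ratio, same order | 5% decision differs |
|---|---|---|---|
| 10% | 88.3% vs 88.3% | 6.46 vs 6.50 | 0.7% of trials |
| 20% | 87.8% vs 87.8% | 6.60 vs 6.68 | 1.3% |
| 33% | 86.7% vs 87.7% | 6.90 vs 7.16 | 2.3% |

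**Sensitivity analyses.** Suppose the image readers disagree on a day-43 photograph. In the worst-case analysis an event at 43 becomes censored at 43, above the cap; if it was the only late event, the fall to 0% disappears. In the best-case analysis a subject censored at 42 becomes an event at 42, while a consensus event seen the same day stays at 43. The third analysis, which censors early discontinuations at 42 days, also leaves event times uncapped.

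**The case against.** The strongest reply is that little inference rests on this. The primary endpoint is a proportion, the Cox results barely move on average, and the Kaplan-Meier plots are displays: section 10.3.2 names no log-rank test, median or day-42 Kaplan-Meier estimate for this endpoint. The fall to 0% comes after day 42, so a plot whose axis stops there would not show it, and the plan does not state the axis. At day 42 the hydrogel curves differ by one event (75% vs 68.75%). Any Kaplan-Meier curve ends at zero when its last observation is an event. All of this stands and limits the severity. What the one-sided cap adds is certainty: once a late event occurs, the fall follows whatever the follow-up of the other subjects.

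The 33% rate corresponds to Visit 7 spread evenly over days 41 to 43. The return to the original weekday makes the lower rates more plausible. That also stands.

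The endpoint's reference to the 6-week period might be read as excluding day-43 events. No rule says so, and Visit 7 readings feed the primary endpoint, so dropping such events would set the secondary endpoint against the primary one.

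Finally, the separate SAP to which section 10 defers was not among the documents supplied and might cap events. If it does, the protocol wording still has to be brought into line.

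**Conclusion.** The concern holds for the text supplied. The rule is stated and, when followed, gives a wrong curve in any plotted group with a first debridement dated after day 42. The fall to 0% is algebraic and needs no assumption beyond that event. Its frequency rests on assumed day-43 rates and constant weekly hazards: roughly 6% to 15% of trials at rates of 5% to 10%, rising to 36% to 41% at 33%. The 68.75% comparator assumes that all 11 un-debrided subjects were followed to day 42 or later. Severity is minor: the damage is mainly in the tail of secondary plots, the average effect on the Cox analysis is small, and the primary analysis is unaffected.

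**What to change.** Replace the truncation sentence in section 10.3.2 with one rule for both kinds of time: event and censored times above 42 days are set to 42, and the same rule applies after any flag change in the sensitivity analyses. Make the SAP match before database lock.

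Truncating neither would also remove the one-sidedness, but the tail would then depend on how many un-debrided subjects happened to be seen on day 43 or later (0% to 68.75% in the hydrogel example). Nominal days (7 to 42) would work only if taken from the scheduled week of the actual visit date, not from the Visit 7 label. Closed ulcers "go directly to Study Visit 7 (Exit Visit), be discontinued from treatment and have exit procedures performed" before week 6 (section 9.1.3), and for discontinued subjects the rule is "In all cases the Exit Visit (Study Visit 7) must be completed" (section 9.2).

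The cost is one sentence, with no change to data collection or operations.

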8.1 STUDY DESIGN

This is a randomized, controlled, parallel observer-blind group study. Subjects providing informed consent will be screened against the inclusion/exclusion criteria. Subjects who meet all of the inclusion criteria and none of the exclusion criteria will be randomly assigned in an equal allocation ratio (1:1) to either SANTYL or to the hydrogel control according to a pre-determined randomization schedule using a blocking technique. Subject randomization will be stratified by the Subject's wound size at baseline resulting in two possible strata: ≥1.0 and ≤10.0 cm²; and >10.0 and ≤64.0 cm². A blocked design will be used for each individual stratum. In either case, caregivers will apply test article once daily (more often as needed for compromised dressing integrity) for up to 6 weeks.

If the ulcer is closed and completely re-epithelialized prior to the end of the 6 week treatment period in either group, the subject will complete Study Visit 7 (Exit) and will be dismissed from the study.

At each weekly visit, the target ulcer will be photographed and area measured using the ImageIQ EDCIQ mobile imaging system. At Study Visit 1 and at Study Visit 7, the ulcer will be assessed using the PUSH and WBS tools. In addition, resource utilization information will be collected at each study visit as described in Section 9.5.

Figure 8.1-1: Study Flow Chart

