9.4.2 Percentage of Necrotic Tissue and "Complete Debridement"

All wound photographs will be reviewed in a blinded fashion, identified only by subject number, initials, and date of assessment by two independent reviewers. The reviewers will complete an assessment form providing the percentage of the ulcer covered by non-viable, neerotic tissue as measured using the ImageIQ EDCIQ mobile imaging system. In any case where one reviewer selects 0% or "complete debridement", and the second reviewer does not, the photograph will be re-reviewed at a consensus meeting.

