Two separate sensitivity analyses will be performed to ensure that the efficacy findings are not reliant on assumptions made in the analysis, derivations, or changes agreed between the blinded review panel. The analysis for the proportion of subjects achieving completed debridement will be repeated with the following modifications using the Full Analysis Set only:

- 1) In cases where there is initial disagreement (pre-consensus meeting) between the two blinded reviewers, the "worst case" value will be used. That is, in cases where one reviewer found the ulcer to have achieved complete debridement whilst the remaining reviewer found there to still be (>0%) necrotic, non-viable tissue present, the following will be imputed:

 Complete debridement achieved = No.
- 2) In cases where there is initial disagreement (pre-consensus meeting) between the two blinded reviewers, the "best case" value will be used. That is, in cases where one reviewer found the ulcer to have achieved complete debridement whilst the remaining reviewer found there to still be (>0%) necrotic, non-viable tissue present, the following will be imputed:

Complete debridement achieved = Yes.

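### The worst-case and best-case reader analyses of time to debridement change the censoring flag but freeze the day, so event and censoring times are wrong whenever a dispute precedes the last visit

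*Combined protocol and SAP*

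**What the plan says.** **Main derivation (protocol section 10.3.2).** A subject who achieves complete debridement has an event at the first visit where it was found, counted from Study Visit 1. For anyone who withdraws or never achieves it, "the time to complete debridement will be censored at the last visit date attended". A further line adds: "Where the censored time to complete debridement is greater than 42 days, this will be truncated to 42 days".

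**Reader sensitivity analyses (section 10.3.1).** The trigger is the same for both: "In cases where there is initial disagreement (pre-consensus meeting) between the two blinded reviewers". The worst case imputes that debridement was not achieved; the best case imputes that it was. The stated purpose is to show that findings do not rest on changes agreed within the blinded panel.

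**Carry-over to time (section 10.3.2).** Both analyses are repeated for time to complete debridement, but the "censoring flag may be modified as detailed previously in the primary analysis, but the time in days will remain unchanged".

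**When disputes arise.** Under section 9.4.2 each photograph has two readings. If one image reviewer records complete debridement "and the second reviewer does not, the photograph will be re-reviewed at a consensus meeting". Section 9.1.2 has subjects assessed weekly from Study Visit 1 to Study Visit 7. Section 8.1 provides for early completion on closure, not on debridement: "If the ulcer is closed and completely re-epithelialized prior to the end of the 6 week treatment period in either group".

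**The concern.** In the main derivation the flag and the day are two outputs of one set of visit-level readings. A different rule for what counts as complete debridement therefore changes both. Holding the day fixed gives pairs of flag and day that the plan's own formulas would not produce:

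- **Worst case, flag flipped.** A subject disputed at day 14, with consensus that debridement was complete, is censored at day 14 although still under weekly observation and, in this scenario, known not to be debrided. Any later visit where both image reviewers agree is lost.
- **Worst case, flag kept** because both agree at day 21. The event stays at day 14, the disputed date.
- **Best case.** A newly imputed event falls at the last visit, not at the visit where one image reviewer called it. A later consensus event cannot move to the earlier single-reader date.

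The text does not say which worst-case reading of the flag applies, so two programmers could obtain different results.

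At stake is whether these runs do their job. When disputed calls are never later agreed, the frozen worst case stays closer to the main result than it should, which is false reassurance from an analysis meant to detect fragility.

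**Working it through.** **Inputs.** Section 11: 85% vs 29%, 16 per arm, 15% drop-out. Sections 9.1.2 and 10.3.2: weekly visits, 42 days. Dispute rates and patterns are assumed, because the documents give none.

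**The plan's own figure.** The disputed clause carries no number. The one design figure is the sample size. Exact two-sided Fisher power at 85% vs 29%, alpha 0.05, is 80.9% with 13 per arm (74.2% with 12), so 26 subjects reproduces if 80% power was intended; the power is not stated. 13/0.85 = 15.3, rounded up to 16 per arm, gives 32.

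**1. Constructed worst case, 16 subjects in an arm.** Four disputed at day 14 with consensus complete, six undisputed events at days 21 to 35, six without event. Proportion debrided at day 42 (Kaplan-Meier):

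- Main analysis: 10/16 = 62.5%.
- As written, flags flipped: the four leave the risk set at day 14, giving 6/12 = 50.0%.
- Re-derived, never agreed later: 6/16 = 37.5%.
- Re-derived, both agree at day 21: 10/16 = 62.5%.
- As written, flags kept because both agree at day 21: the day-14 estimate is 4/16 = 25.0%, against 0% re-derived.

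The frozen 50.0% is too high in one pattern and too low in the other.

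**2. Constructed best case, 16 subjects.** Four consensus events by day 21, six overruled single-reader calls at day 21, six without event.

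- As written, day 21: 4/16 = 25.0%. The six events fall at day 42, giving 1 − (12/16)(6/12) = 62.5% there; median day 42.
- Re-derived, day 21: 10/16 = 62.5%; median day 21.

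**3. Closed form, worst case, disputed events never later agreed (the two flag readings coincide).** No drop-out and a constant weekly hazard h = 1 − (1 − p)^(1/6), giving h = 0.271 for p = 0.85 and 0.055 for p = 0.29. With share q of events disputed, day-42 values are:

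- as written: 1 − (1 − (1 − q)h)^6
- re-derived: (1 − q)p

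| q | SANTYL as written | SANTYL re-derived | Difference between arms, as written | Difference, re-derived |
|---|---|---|---|---|
| 10% | 81.3% | 76.5% | 54.9 points | 50.4 points |
| 20% | 76.9% | 68.0% | 53.1 points | 44.8 points |
| 40% | 65.5% | 51.0% | 47.1 points | 33.6 points |

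The main-analysis difference is 85 − 29 = 56.0 points.

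**4. Simulated Cox model, worst case.** 2,000 trials, 16 per arm, 15% drop-out, 20% of events disputed, Efron ties, likelihood-ratio test.

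- Never agreed: median hazard ratio 5.60 as written, 4.64 re-derived, 5.79 main. A separate run gave 5.37, 4.48 and 5.47, the same pattern.
- Always agreed a week later: 5.76 with the flag flipped, 5.95 with it kept, 5.93 re-derived. The chance of significance is 85.9%, 93.2% and 92.7% respectively, so any loss of power depends on the reading.

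**5. Simulated reading errors.** 1,500 trials without drop-out. Each image reviewer detects true debridement with probability 0.90 and wrongly calls it with probability 0.02 at each visit; consensus is taken as correct. Day-21 Kaplan-Meier, SANTYL arm (main 60.9%):

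- Worst case: 57.4% re-derived; as written, 60.9% with the flag set from all visits or 52.6% with it flipped at the disputed first event.
- Best case: 65.3% re-derived, 60.9% as written. Hydrogel: 25.4% and 15.9%. The difference between arms is 65.3 − 25.4 = 39.9 points re-derived and 60.9 − 15.9 = 45.0 as written.

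**The case against.** The clause can be read as a deliberate exception for named sensitivity runs, not a contradiction: hold the day and test the flag. The sentence that censors early discontinuers at day 42 also departs from the main rule. The plan does not expressly ask for Kaplan-Meier plots or medians in these runs; its planned estimate is a hazard ratio. The large gaps need ulcers judged complete at consensus that both image reviewers never agree on again, and no rate in the documents supports that. In the constructed best case only the timing differs, since both methods reach 62.5% at day 42. The analysis is a sensitivity check on a secondary endpoint, and the separate SAP, which might settle the flag rule, is not in the reviewed text.

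Much of this stands as a limit on size. The effect could be near zero if second readings catch up within a week, and the direction depends on an unstated reading. It does not remove the defect. A rule stated on purpose can still produce wrong times, and the proportional hazards model uses those times. In a time-to-event analysis a shift in timing is a shift in the result. The plan also treats the parallel case differently: for percentage of non-viable tissue, section 10.3.2 takes the higher or lower reading separately at every assessment.

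**Conclusion.** The concern holds: the clause is wrong as written for any dispute before a subject's last visit. Disputes at the last visit are essentially unaffected, apart from a trivial 42-day truncation effect from the one-day visit window. The error can go either way. It depends on the dispute pattern and, in the worst case, on how the flag is set.

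All sizes rest on assumed dispute patterns. With 10% to 40% of consensus events disputed and never later agreed, the worst-case difference between arms is overstated by 54.9 − 50.4 = 4.5 to 47.1 − 33.6 = 13.5 points. With agreement one week later, the hazard ratio is nearly unchanged. The primary analysis, its own reader sensitivity analyses and the sample size are not affected. This should be corrected, but it does not threaten the trial's main conclusion.

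**What to change.** Replace the clause in protocol section 10.3.2, and match it in the SAP, with a rule of this kind:

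> For each scenario, re-derive both the event indicator and the time from the pre-consensus readings. Worst case: the event is the first visit at which both image reviewers independently scored complete debridement. Best case: the first visit at which either did. Otherwise censor at the last visit attended, truncated at 42 days. Treat missing photographs and closed ulcers as in the main analysis of this endpoint.

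Section 10.3.2 borrows the primary definition of complete debridement, which carries forward the last observation for missing photographs, but it gives no explicit rule for ulcers that close. The SAP should state that rule once, for the main and the sensitivity runs alike.

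The report should not describe these runs as bounding the treatment effect. Both arms are imputed in the same direction, so they bound each arm's curve only.

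The cost is one clause and its programming. No new data are needed, because the primary sensitivity analyses already require both image reviewers' pre-consensus readings, and the SAP is to be finalized before database lock.
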